Participants who meet inclusion/exclusion criteria will be randomized into a study condition and will be assigned to a project therapist. Because most VAMC patients who meet study criteria likely will present with multiple depressive/anxiety disorders (Brown et al., 2001), principal diagnosis, or the most impairing of the diagnosable disorders, will be used to inform randomization. Principal diagnosis will be determined via diagnostic severity scores in the Anxiety Disorders Interview Schedule-5 (ADIS-5) (Brown, 2014). To balance diagnoses across the two conditions, a stratified random assignment based on principal diagnosis will be used (MDD, PTSD, and PD/AG) ([name], 2015). Based on referrals to the PI's CDA, it is expected that at least 45% of the recruited Veterans will have served in OEF/OIF and $\geq 50\%$ will be representative of minority groups.

Eligible VAMC patients will be randomized into one of two treatment conditions: TBT or DSTs. Both treatment conditions will include 12 weekly 45- to 60-minute treatment sessions. Both treatment conditions will be delivered either in-person and via VA-approved telehealth technologies, based upon the preference of the participant. The general format of sessions will involve: 1) brief check-in; 2) review of materials from previous sessions; 3) review of homework assignments; 4) overview of new materials and in-session exercises; and 5) assignment of homework for next session. Attendance and homework completion will be recorded.

Randomization Procedures

Participants will be randomly assigned (1:1) to one of the two study arms ($n = 108$ per arm) using a permuted block randomization procedure. Randomization will be stratified by diagnostic group (PTSD, PD/AG, MDD) and block size will be varied to minimize the likelihood of unmasking. After determining eligibility and completing consent and baseline assessment materials, enrolled participants will be assigned to their treatment condition by the Research Project Therapist/Coordinator using a computer-generated randomization scheme. Once a participant is randomized, they will be included in the modified intent-to-treat (MITT) analysis. The Research Project Therapy/Coordinator and the statistical analyst in charge of randomization ([name]) will be the only

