research team members aware of the randomization assignment. Randomization will occur at the participant level. As such, we will take the following steps to minimize contamination between the two arms of the study: 1) only one member of a household will be eligible for enrollment; and 2) other VA providers will be informed of their patients' participation in the study, but will be blinded to the treatment condition. Although some variability is expected due to the varying prevalence rates of PTSD, PD/AG, and MDD in Veterans, recruitment strategies will be adjusted accordingly if any of the three disorder groups is under-represented (e.g., recruit more heavily in PTSD clinic if PTSD is under-represented).

DSTs Control Condition Matching and Assignment

To provide an evidence-based comparison for the TBT condition, DSTs will be used that are matched to the participant's most severe diagnosis, based upon the average of the ADIS interference and distress scores. If the scores are equivalent for two or more diagnoses, participants will be asked to list which diagnosis/symptoms that they find most impairing. DSTs will be included for each of the three targeted diagnoses, including PTSD (CPT for PTSD), PD/AG (CBT for PD/AG), and MDD (CBT for MDD). Each of these DSTs have published manuals for administration and have received extensive support in the literature (Barlow, 2014). Although several DSTs are available for each disorder (e.g., PE for PTSD, applied relaxation for PD/AG, and behavioral activation for MDD), these three DSTs were selected based on their similarities in cognitive-behavioral techniques as well as their robust evidence in the literature. In addition, all three DSTs have been shown to improve comorbid symptomatology and therefore may be a more accurate comparison to TBT as compared to other available DSTs that may have less effect on comorbidity (e.g., applied relaxation for PD/AG) (Nishith et al., 2005; Tsao et al., 2002).

Treatment Training and Fidelity

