For all study outcomes (ADIS-5, IIRS, PCL-5, PDSS, PHQ-9, and STICSA), Veterans will be randomly assigned (1:1) to the TBT and specific DST conditions. The power analysis was calculated to be powered at 80% with a Bonferroni-corrected 1-tailed $\alpha = .006$ (.025/4 primary outcomes) to detect non-inferiority for TBT in comparison to the aggregated DST effect. Meta-analyses for CBT for MDD, CPT for PTSD, and CBT for PD/AG reveal large treatment effects (CBT for MDD bias-adjusted $g = .53$; Cuijpers et al., 2013; CPT for PTSD in military personnel $g = 1.33$; CBT for PD $g = 0.35$; Hofmann & Smits, 2008). Thus, the average effect size for DSTs was expected to range from small-to-medium to large. A power analysis was conducted using procedures recommended by Chow, Shao, and Wang (2017), Flight and Julious (2014), and Julious (2004) as well as recommendations by the United States Food and Drug Administration and the European Medical Association (Food and Drug Administration, 2017). An important topic in non-inferiority designs is selection of the “appropriate” prespecified non-inferiority limit. Current best practice involves selecting a non-inferiority margin that is not greater than the smallest effect size expected for the DSTs in comparison to a control condition. As a tradeoff between sample size needs and feasibility of recruitment, we conducted power analysis setting the non-inferiority margin to 0.5, indicating that we would consider TBT non-inferior to the DSTs if TBT were to perform less than half a standard deviation worse than the DSTs. We set the expected group different to 0.3 given our pilot data demonstrating that TBT outperforms DSTs by this margin across primary outcome variables. Using procedures recommended by Chow, Shao, and Wang (2017) for non-inferiority designs, which utilize the pre-specified non-inferiority margin (here prespecified as $\Delta d = 0.5$) and the estimated effect in the active comparison treatment ($d = 0.3$), we determined that 144 participants (72 per cell) would be needed. However, this does not account for potential attrition or for potential design effect issues involving therapist effects or for potential missing data related to telehealth delivery of services. To account for possible attrition and missing data as well as the potential influence of design effects, we increased the sample size to 306 participants based on the data available to date. Based on pilot data, we expect to find large within-person effects ($d \geq .80$) for TBT, indicating 4/5ths of a SD reduction in each of the primary outcome measures. This sample size would leave us powered to detect small-to-medium within-person effect sizes.

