The continuous measures included measures of disorder severity scales (ADIS-5), disorder-specific symptomatology (PCL-5, PDSS, PHQ-9, and STICSA), general related symptomatology (STISCA), and quality of life and impairment (IIRS). Of these variables, the PCL-5, PDSS, PHQ-9, and STICSA are the primary outcomes of interest. All other analyses will be conducted in an exploratory fashion to inform future studies and compare findings to previous studies ([name], 2014; [name] et al., 2017; 2019). Parameter estimates to calculate the effect size difference will be arrived at using three-level (measurement occasions nested within participants nested within assigned treatment condition) generalized mixed-effects regression models (MRM). MRM is a method of repeated measures analyses that allows for modeling of continuous and categorical independent and dependent variables and for appropriate modeling of covariance structures when observations are correlated across time and/or across condition. This analytic approach fully captures variability in outcomes across multiple follow-up assessments and accounts for any potential effect of the group to which a participant is assigned and is thus preferred over methods that collapse data over time. We will calculate between-group treatment differences as Cohen's d, based on the effect of treatment condition on the intercept parameter when the model is centered on post-intervention and on the effect of treatment condition on the intercept parameter when the model is centered on month 6. We prespecified the non-inferiority margin (d) to be 0 (indicating we expected TBT to be at least equivalent to the aggregate DST effect) and the one-sided CI for our four primary analyses at $\alpha = .006$. In the primary analyses of outcome variables, we will covary for the baseline value of the variable of interest. We also will include the linear effect of time as well as a time by condition interaction effect to determine whether treatment differences (or lack thereof) were stable from post-intervention through the follow-up. Additional covariates (e.g. age, number of psychiatric comorbidities, race, sex, combat theatre, number of treatment sessions, specific DST received) will be added to the model to adjust for putative confounding variables. Effect size CIs that do not contain 0 provide evidence in support of noninferiority for TBT. The primary outcome time point is at the end of the active treatment phase and the secondary time point is at the end of the naturalistic 6-month follow-up period. Further, within-subject effect sizes from baseline to post-intervention and to 6-month follow-up also will be calculated within the TBT condition to quantify TBT-specific reductions in symptoms. These analyses will be probed to examine potential therapist effects. First, design effects will be calculated for the primary outcome variables. Design effects > 2 are often used as a heuristic to judge when these effects can be problematic.

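### The primary model does not prespecify the randomisation stratum (principal diagnosis), and the nearest covariate it lists exists in the DST arm only

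*Combined protocol and SAP*

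**What the plan says.** The Randomization Procedures section states: "Randomization will be stratified by diagnostic group (PTSD, PD/AG, MDD) and block size will be varied". The Procedures section gives the purpose, which is to balance diagnoses between the two conditions: "a stratified random assignment based on principal diagnosis will be used".

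The Efficacy Measures Analyses (Primary Aim) section fixes three elements of the primary model besides treatment condition. The first is the baseline score: "In the primary analyses of outcome variables, we will covary for the baseline value of the variable of interest". The other two are time terms: "We also will include the linear effect of time as well as a time by condition interaction effect".

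It then gives an open, e.g.-type list of further covariates that ends: "number of treatment sessions, specific DST received) will be added to the model to adjust for putative confounding variables". Neither principal diagnosis nor the randomisation stratum appears in that list or elsewhere in the analysis plan.

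The section on DST matching ties one DST to each diagnosis: "DSTs will be included for each of the three targeted diagnoses, including PTSD (CPT for PTSD", with CBT for PD/AG and CBT for MDD as the other two. Only participants randomised to the DST arm receive one.

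**The concern.** Blocking within strata keeps the arms balanced on diagnosis, so differences between strata add almost nothing to the true sampling error of the arm difference. A model without the stratum leaves those differences in the residual, and its standard error is then larger than the design warrants. PCL-5, PDSS and PHQ-9 each measure the disorder that defines one stratum, and the comparator therapy also differs by stratum. Some difference remaining after baseline adjustment is therefore plausible on those three. At stake is the precision of the bounds that decide non-inferiority at a one-sided alpha of .006.

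The DST-received covariate does not fill the gap. It is the listed term closest to diagnosis, but it is undefined in the TBT arm, and entering it changes what the treatment coefficient estimates.

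**Working it through.** **Inputs from the documents.** Total 306, allocated 1:1, so 153 per arm (the Randomization Procedures section says 108 per arm, which conflicts with 306). Three strata. One-sided alpha .006, so z = 2.512. The sample-size section gives the target comparison (the quote starts just after a decimal point): "025/4 primary outcomes) to detect non-inferiority for TBT in comparison to the aggregated DST effect".

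**Assumptions.** Strata of equal size: 102 each, 51 per arm. R² is the share of post-treatment variance, after baseline adjustment, that diagnosis explains. The documents do not give it, so the range shown is 0 to .20.

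**The plan's own figure.** The plan gives no figure for the effect of the stratum. Its sample size of 72 per arm is not a usable starting point for power. With n = 2(2.512 + 0.842)²/δ² = 22.50/δ², a distance δ from the margin of 0.5 gives 90 per arm, 0.5 − 0.3 = 0.2 gives 563, and 0.5 + 0.3 = 0.8 gives 36.

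**Step 1: width of the bound.** The reported SE is too large by the factor 1/√(1 − R²). The actual one-sided error is 1 − Φ(2.512/√(1 − R²)). The half-width without the stratum is 2.512 × √(2/153) = 0.287 SD; with it, this is multiplied by √(1 − R²).

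| Assumed R² | Bound too wide by | Actual one-sided error | Half-width with stratum (SD) |
|---|---|---|---|
| 0 | 0% | .0060 | 0.287 |
| .02 | 1.0% | .0056 | 0.284 |
| .05 | 2.6% | .0050 | 0.280 |
| .10 | 5.4% | .0040 | 0.272 |
| .20 | 11.8% | .0025 | 0.257 |

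**Step 2: what those R² values require.** Suppose one of three equal strata differs from the others by g residual SDs. Then R² = (2g²/9)/(1 + 2g²/9). A gap of 0.3 gives .02, 0.5 gives .05, 1.0 gives .18, and 1.06 gives .20.

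**Step 3: check by simulation.** Settings: 153 per arm, an assumed baseline gap of 1 SD in one stratum, baseline-outcome correlation .5, 1,500 runs per setting. For residual diagnosis effects of 0, 0.3, 0.5 and 1.0 SD, the baseline-only SE was 1.00, 1.01, 1.03 and 1.11 times the stratum-adjusted SE. The actual spread of the estimate hardly differed between the two models up to 0.5 SD (0.0975 against 0.0974 at 0.3 SD). The baseline-only bound is therefore conservative, and the estimate is not biased.

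**Step 4: the DST-received term as listed.** Code it with levels in the DST arm only, beside the condition term.
- Without the stratum, the treatment coefficient compares all TBT participants with one reference DST. Its SE is √(1/153 + 1/51) = 0.162, against √(2/153) = 0.114, about 41% larger. The simulation, which also adjusts for baseline, gave 0.099 rising to 0.144, about 45%. The estimate moved by about 0.18 SD when the residual diagnosis effect was 0.3 SD.
- With the stratum also in the model, the two terms together form a full treatment-by-stratum interaction. The coefficient is then a contrast within one reference diagnosis, with SE √(2/51) = 0.198 against 0.114, a ratio of √3 = 1.73.

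Neither is the comparison with the aggregated DST effect that the plan sets out to make.

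**The case against.** **The list is open.** The plan does not say that diagnosis will be left out. Further covariates are to be added, and one of them follows from the diagnosis. If the authors mean the DST matched to each participant's diagnosis in both arms, that variable is the stratum. This stands to the extent that a reader who infers that the primary model adjusts only for the baseline score goes beyond the text. The supportable statement is that the stratum is not prespecified. As worded, the covariate is the therapy received, and TBT participants receive no DST.

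**The effect may be very small.** Baseline PCL-5, PDSS and PHQ-9 already carry much of the difference between diagnoses, and the plan expects most participants to have several of these disorders. Both points stand. An R² of .20 needs a residual gap above 1 SD, and a gap of 0.3 SD widens the bound by only 1%.

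**It need not touch every outcome.** A reader might infer that the bounds for all four primary outcomes are too wide. The argument from disorder-specific scales covers three; the plan describes STICSA as measuring transdiagnostic anxiety, so it may gain least.

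**The margin matters more.** The sample-size section sets the margin at 0.5 and the analysis section at 0. That gap of 0.5 SD compares with 0.003 to 0.015 SD of half-width for R² of .02 to .10. This stands as a ranking of the two problems, but it does not answer this one.

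**Conclusion.** The point holds as a gap in prespecification with a modest cost in efficiency. The randomisation stratum is not a stated term of the primary model, and the listed covariate closest to it is defined in one arm only. The bound is 0% to 11.8% too wide over an assumed residual R² of 0 to .20, and 1% to 5.4% over .02 to .10.

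A reader might infer that the omission threatens the validity of a non-inferiority claim. It does not: the actual one-sided error is at or below .006. Nor can one power loss be quoted. As an illustration only, with 153 per arm, a margin of 0.5 and a true difference of 0, adding the stratum moves power from 97.0% to 97.2% (R² .02), 97.2% to 97.6% (.05) or 97.5% to 98.2% (.10). With a margin of 0 and a true difference of 0, the chance of success is at most .006 under either model.

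The larger risk is the DST-received term. Entered as listed, it changes the contrast and raises the SE by about 41% to 45% alone, or about 73% with the stratum. These figures assume equal strata and DST-arm-only coding.

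**What to change.** In the Efficacy Measures Analyses section, state that the primary model for each of the four primary outcomes includes fixed effects for the randomisation stratum (PTSD, PD/AG, MDD, as used to randomise) in both arms, beside the baseline score, for the post-treatment and 6-month contrasts. In the same edit, remove the specific DST received from the primary model. The two changes belong together, because adding the stratum while keeping that term gives the 73% increase in SE.

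The cost is two degrees of freedom and a short change of wording. No new data are needed, since the stratum is recorded at randomisation. Any statement of the resulting power should wait until the two margins are reconciled.

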The primary goal of the proposed study is to compare TBT and matching DSTs in a large, randomized investigation in a Veteran sample via a non-inferiority design. The study will use a repeated measures RCT design to compare TBT to DSTs in 306 Veterans with PTSD, MDD, panic disorder and/or agoraphobia (PD/AG) and related symptoms of depression/anxiety and impairments. DSTs will be matched to participants' targeted diagnosis (e.g., Cognitive Processing Therapy for PTSD, CBT for MDD, and CBT for PD/AG). Assessments of disorder-specific symptomatology, as well general symptoms of the depressive/anxiety disorders and related impairments, will be used due to the transdiagnostic approach and related research aims of the proposed study. Assessments will be completed at baseline, mid-treatment, immediate post-treatment, and 6-month post-treatment follow-up. Process variables (satisfaction, attendance, discontinuation rates) also will be recorded.

Primary Aim: To examine efficacy of TBT on improving psychiatric symptomatology and related impairments in Veterans with depressive/anxiety disorders compared to DSTs.

Hypothesis: TBT will result in non-inferior improvements in psychiatric symptomatology, as assessed by the PTSD Checklist for PTSD, PHQ-9, Panic Disorder Severity Scale for PD/AG, and transdiagnostic anxiety on the State Trait Inventory for Cognitive and Somatic Anxiety and transdiagnostic impairment on the Illness Intrusiveness Rating Scale, compared to the DST control conditions.

Secondary Aim: To examine feasibility and acceptability of TBT

Hypothesis: TBT will be well tolerated by Veterans as demonstrated by improved attendance (number of weeks to complete treatment), treatment discontinuation rates (yes/no), and patient satisfaction questionnaires, as assessed by the Satisfaction with Therapy and Therapist Scale – Revised, as compared to the DSTs.

B. BACKGROUND AND SIGNIFICANCE

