In addition to the unfunded pilot trials, [name] CSR&D CDA funded a small RCT to compare TBT with one specific individual DST, behavioral activation (BA), in Veterans with depressive/anxiety disorders. The study originally targeted a sample of 36 per group; however, the management of the grant and referral process allowed for a larger than expected sample to better test the hypotheses within the original timelines (TBT $n = 44$; BA $n = 46$). In contrast to the proposed study, this small RCT was designed to provide initial findings for TBT via an RCT with a single comparison group to inform future investigations. Results demonstrated reductions in outcome variables from pre-treatment to post-treatment for those in TBT. Large effects were found across all outcome variables. To examine the effects of treatment on several outcome variables (Table 5), linear mixed regression models were conducted using an intent-to-treat approach and handling missing data via robust maximum likelihood. Results revealed significant treatment effects from pre-treatment through 6-month follow-up, that were qualified by marginal to significant group by session effects for depression, anxiety, and somatic anxiety such that participants receiving TBT showed greater treatment gains on these outcome variables than did participants receiving BA. Although not significant, all other outcome variables favored TBT as well.

Table 5: Comparison of TBT and Behavioral Activation in Veterans with Depressive/Anxiety Disorders

	DASS-Stress B (SE)	DASS-Depression B (SE)	DASS-Anxiety B (SE)	STICSA-Cognitive B (SE)	STICSA-Somatic B (SE)	PCL-PTSD B (SE)	IIRS-Impairment B (SE)
Intercept	10.73* (0.76)	9.65* (0.87)	7.73* (0.82)	24.82* (1.04)	20.49* (1.02)	38.29* (2.56)	50.01* (2.44)
Group	-0.71 (1.06)	0.49 (1.10)	-1.39 (1.06)	-1.82 (1.34)	-1.64 (1.28)	-3.27 (3.45)	1.72 (3.53)
Session	-3.19* (0.67)	-3.54* (0.71)	-2.69* (0.61)	-5.08* (1.10)	-3.18* (0.62)	-10.27* (2.32)	-11.76* (2.19)
GrpXsess	0.62 (0.88)	1.49* (0.90)	1.59* (0.73)	1.89 (1.35)	1.66* (0.90)	3.43 (2.70)	1.69 (2.82)

Note. Intercept is centered on baseline session. GrpXsess = Group by session (baseline, post-intervention, 6-month follow-up [0, 1, 2]) interaction. * $p < .05$, † $p < .10$.

D. RESEARCH DESIGN AND METHODS

Table 6: Project Timeline

Proposed Component	Year	Timeframe
Preparing for RCT	Y01	month 01 – 06
Hiring staff	Y01	month 01 – 03
Training on procedures/protocols	Y01	month 03 – 06

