Participant assessments may be completed either in person, via USPS mailed questionnaire packets and accompanying self-addressed, stamped envelope to be mailed back to the project team, or in Qualtrics or VA Redcap. Redcap and Qualtrics are VA-approved programs for survey data collection. The VA provides a national license to use these programs which will be obtained by the researchers. These programs will be used to implement the surveys and are optimized for computer, smartphone, and tablet. HIPAA compliant data will be utilized and accessed by authorized users on the study who will download this data on the secure research network drive.

Participants will be compensated \$40 for pre-treatment, \$60 for mid-treatment, \$80 for post-treatment, and \$120 for 6-month follow-up for completion of assessment procedures for a total of \$300 for the entire study. Payments will be made via VA direct deposit. To reduce the likelihood of missing data, all assessments will be scheduled separately from normal treatment sessions. Assessments of disorder-specific symptomatology, as well general symptoms of the depressive/anxiety disorders and related impairments, were chosen due to the transdiagnostic focus of the proposed study ([name], 2015). All assessments will be completed by the Project Research Recruiter and Assessor. Additional training will be required prior to administration of the diagnostic interview (ADIS-5). The assessor will be required to observe the PI administer the ADIS-5 twice and then administer the ADIS-5 twice themselves under the direct observation of the PI. The assessor will be blinded to treatment condition and supervised by the PI. ADIS-5 assessments will be recorded to investigate inter-rater reliability of diagnoses, with 20% of recordings being re-assessed by an external ADIS-trained assessor after the participant has completed all study procedures, with feedback provided to the assessor throughout the duration of the study to improve reliability. In addition to the four assessment points, select measures (PHQ-9, PDSS, and PCL-5) will be administered every other treatment session to monitor safety and treatment progress.

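### The primary model uses linear time without naming its outcome occasions; if mid-treatment scores enter, the post-treatment contrast can be biased in either direction

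*Combined protocol and SAP*

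**What the plan says.** Section D, Efficacy Measures Analyses (Primary Aim), expresses the arm difference as Cohen's d, "based on the effect of treatment condition on the intercept parameter when the model is centered on post-intervention", and again with the model centred on month 6. On time it says "We also will include the linear effect of time as well as a time by condition interaction effect", with the purpose "to determine whether treatment differences (or lack thereof) were stable from post-intervention through the follow-up". On baseline it says "we will covary for the baseline value of the variable of interest". On timing: "The primary outcome time point is at the end of the active treatment phase", with 6 months as the secondary time point.

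The section does not list the assessments that form the outcome vector, and it gives no unit for time (weeks or visit number). The schedule offers more than two candidates. The opening summary says "Assessments will be completed at baseline, mid-treatment, immediate post-treatment, and 6-month post-treatment follow-up", and the assessment section adds that "select measures (PHQ-9, PDSS, and PCL-5) will be administered every other treatment session". Those three scales are three of the four primary outcomes.

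**The concern.** With two occasions, a straight line for each arm passes through both means, and the intercept at post-treatment is the post-treatment difference. With three or more it need not be. The fitted line borrows from every visit, and the intercept is a weighted average of the arm differences at all of them.

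An analyst could include mid-treatment, or the every-other-session scores, and still comply with the text. The primary non-inferiority contrast would then depend on an undocumented choice and might not estimate the difference at the declared primary time point.

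**Working it through.** The documents give no figure for this point, so there is none to reproduce.

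**Inputs.** Mid-treatment is session 6 (Sources of Materials), and treatment is 12 weekly sessions (Procedures). I take mid-treatment as week 6, post as week 12 and follow-up as week 12 + 26 = 38. This is an assumption, since up to 18 weeks is allowed. Visit-number coding (1, 2, 3) is shown as the alternative. Differences are in SD units, positive when TBT is worse. The profiles over visits are assumptions, because the documents do not describe one.

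**Formula.** For complete, balanced data with a random intercept (with or without a random slope), the weight of visit i in the fitted difference at post is

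w_i = 1/k + (t_post − t̄)(t_i − t̄)/S, where S = Σ(t_i − t̄)².

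**Post and 6 months only.** t̄ = 25, S = 13² + 13² = 338.
- Post: 1/2 + 169/338 = 1.00
- 6 months: 1/2 − 169/338 = 0

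Nothing is averaged.

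**Mid, post and 6 months, in weeks.** t̄ = 56/3 = 18.67; deviations −12.67, −6.67, 19.33; S = 160.44 + 44.44 + 373.78 = 578.67.
- Mid: 0.333 + 84.44/578.67 = 0.479
- Post: 0.333 + 44.44/578.67 = 0.410
- 6 months: 0.333 − 128.89/578.67 = 0.111

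With visit-number coding the post visit sits at the mean, so each weight is 1/3.

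**Every-other-session scores plus 6 months** (weeks 2, 4, 6, 8, 10, 12, 38). t̄ = 80/7 = 11.43, S = 893.7. Post weight: 1/7 + 0.571²/893.7 = 0.14.

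**Fitted difference at post when the true value is 0.50:**

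| Assumed difference at mid / post / 6 months | Weeks | Visit number |
|---|---|---|
| 0.50 / 0.50 / 0.50 | 0.50 | 0.50 |
| 0.25 / 0.50 / 0.50 | 0.38 | 0.42 |
| 0.25 / 0.50 / 0.25 | 0.35 | 0.33 |
| 0.25 / 0.50 / 0.75 | 0.41 | 0.50 |
| 0.75 / 0.50 / 0.50 | 0.62 | 0.58 |
| 0.50 / 0.50 / 0.75 | 0.53 | 0.58 |
| 0.75 / 0.50 / 0.25 | 0.59 | 0.50 |

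For example, 0.479 × 0.25 + (0.410 + 0.111) × 0.50 = 0.38, and 0.479 × 0.75 + 0.521 × 0.50 = 0.62. Mixed models fitted to simulated data (153 per arm, random intercept, baseline covariate) agreed with the formula within simulation error.

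**What sets the sign.** In weeks, the bias is 0.479(d_mid − d_post) + 0.111(d_6mo − d_post). It is zero when the difference is linear in coded time, because the weighted mean of the visit times is the post time: 0.479 × 6 + 0.410 × 12 + 0.111 × 38 ≈ 12. Curvature common to both arms cancels in balanced data. Only non-linearity in the between-arm difference matters.

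**The case against.** The strongest reply is that the two-occasion reading is the natural one. The interaction is there to judge stability between post-treatment and follow-up, the model is centred at those two points, and baseline is a covariate. Collecting four assessments does not put four into this model. This stands: under that reading the contrast is unbiased. But the sentence gives a purpose for the interaction and does not list the modelled occasions, so the other reading stays open.

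A reader might go further and infer that linear time necessarily shrinks a true TBT deficit and so favours non-inferiority. The documents do not support that, for three reasons.
- The table shows enlargement as readily as shrinkage, and nothing in the plan says how the TBT–DST difference moves over visits.
- A general pull towards zero would need baseline, where randomization makes the expected difference zero, as an outcome occasion. The plan only covaries it. The Table 5 note, "Group by session (baseline, post-intervention, 6-month follow-up [0, 1, 2]) interaction", describes an earlier trial whose intercept was centred on baseline, so it does not set the coding here.
- Any false-positive rate would rest on an assumed profile and on the margin of 0.5 in the sample-size section. The efficacy section sets the margin at 0. There, shrinking a deficit towards zero does not carry it past the margin, and shrinking a true TBT advantage works against the claim. That conflict between the margins needs its own resolution.

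**Conclusion.** The concern holds as a gap in the specification. The plan fixes a linear time term but leaves open the occasions and the time metric on which the meaning of the primary contrast depends. With post and 6 months only, the bias is nil. With mid-treatment added, the post visit carries a weight of 0.33 to 0.41. Over the assumed profiles, a true difference of 0.50 SD is estimated at anywhere from 0.33 to 0.62. With the every-other-session scores plus 6 months, the post weight falls to 0.14.

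These sizes rest on complete balanced data, the week or visit-number coding shown, and profiles that are not in the documents. No direction and no error rate can be claimed. The change should still be made, because the primary contrast ought not to depend on an unstated choice.

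**What to change.** In the efficacy section, name the outcome occasions as mid-treatment, post-treatment and 6 months. Replace linear time with visit as a categorical factor plus condition-by-visit interaction. Use baseline as a covariate only and an unstructured within-person covariance. Take the post-treatment contrast as primary and the 6-month contrast as secondary. Whether the difference is stable after treatment can be read from the change between those two contrasts.

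The cost is a wording change and a few extra parameters, with no new data. If two occasions were always intended, what the post contrast estimates does not change. If more were intended, the bias goes. In either case, observed mid-treatment scores can inform the likelihood for participants who miss the post-treatment assessment.
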